2.1. Study Synopsis

Title	Randomized Controlled Clinical Trial of Non-invasive Device to Alleviate Symptoms of Carpal Tunnel Syndrome
Study Description	Sham-controlled, multi-center and remote patient-centered randomized controlled clinical trial to investigate the efficacy of a novel non-invasive, unobtrusive study device in reducing symptoms of carpal tunnel syndrome (CTS). Daily wear of the study device is expected to significantly reduce symptom severity (evaluated by the Boston Carpal Tunnel Questionnaire) in mild to severe CTS-diagnosed patients. Subjects are randomized into the active device group or sham group for 8 weeks, then followed for 12 weeks post-treatment.
Objectives	Primary: Investigate whether daily wear of the study device significantly reduces patient-reported CTS symptom severity. Secondary: Determine whether there is a difference between the active device group and sham group. Investigate whether changes in symptoms are sustained or continue post-treatment.
Endpoints	Primary: BCTQ-SSS of the treatment group at 8 weeks compared to Baseline. Secondary: BCTQ-SSS at 8 weeks and at post-treatment timepoints between the treatment and sham groups
Study Population	Sample size: 102 (51 in each arm) Adults diagnosed with mild to severe CTS, ages 21-65 of any gender Any geographic location within the United States
Phase	Confirmatory/pivotal
Sites	At least 3 physical sites located in the United States (national enrollment)
Study Device	Stiffness-optimized thermoplastic curved band that has a strong biocompatible adhesive in the center of the concave side of the device. Device is designed to decompress the median nerve and thus relieve symptoms of carpal tunnel syndrome.
Study Duration	Approximately 12 months
Participant Duration	5 months

2.2. Schedule of Events (SOE)

Schedule of Events Table – Active Device Group

Wks Into Study	Treatment Period (8wk)					Post-Treatment Period (12wk)					
	0	2	4	6	8	10	12	14	16	18	20
Enrollment ¹	X*										
NCS ²	X*										
BCTQ ³	X*	X*	X*	X*	X*		X*		X		X
Follow-up ⁴		X*	X*	X*	X*		X*		X		X
Usage Diary ⁵		X*	X*	X*	X*						
User Survey ⁶					X*						
Day	0	14	28	42	56	70	84	98	112	126	140

Schedule of Events Table – Sham Device Group

[figure not shown]
Wks Into Study	Treatment Period (8wk with Sham Device)					Post-Rx Period	Treatment Period (8 wk with Active Device)				
	0	2	4	6	8		10	12	14	16	18
Enrollment ¹	X*										
NCS ²	X*										
BCTQ ³	X*	X*	X*	X*	X*		X*	X	X	X	X
Follow-up ⁴		X*	X*	X*	X*		X*	X	X	X	X
Usage Diary ⁵		X*	X*	X*	X*			X	X	X	X
User Survey ⁶					X*						X
Day	0	14	28	42	56	70	84	98	112	126	140

* = required

- 1 - Enrollment includes completing ICF and baseline questions (eligibility check, CTS diagnosis/history, randomization, demographics, medical history)
- 2 - NCS within 24 months required to enroll
- 3 - BCTQ incorporated into Follow-up Surveys
- 4 - Follow-up Surveys completed by patient online
- 5 - Usage Diary completed online by patient DAILY
- 6 - User Feedback Survey (feedback on design and use of device) completed by patient online.

2.3. Study Procedures Flow-chart

See next page

3. INTRODUCTION

3.1. Background & Rationale

Carpal tunnel syndrome (CTS) is one of the most common peripheral neuropathies and the most well-known workplace repetitive stress injury.¹⁻⁴ The carpal tunnel is located at the wrist and is composed of the eight carpal bones and the transverse carpal ligament. The median nerve travels through the carpal tunnel at the wrist and may become entrapped due to inflammation, awkward wrist postures, repetitive hand motions, or other causes. Compression impairs normal median nerve function, which leads to paresthesia, pain, numbness, and other symptoms in the distribution of the median nerve. Chronic compression may lead to irreversible nerve damage, significant impairment of hand function, and muscle atrophy.^{1,4}

Commonly, CTS is first addressed with conservative treatment options, including wearing wrist braces or splints, lifestyle changes, or the use of oral non-steroidal anti-inflammatory agents (NSAIDs).³⁻⁶ Although wrist splints are prescribed at night and as much as possible during the day, fulltime compliance is poor.⁷ Patients may elect to receive a steroid injection into the wrist, but the procedure is hazardous³ and the effects are short-term. Repeat injections are not recommended.

Severe cases of CTS are often referred directly to surgery to prevent further nerve damage. Approximately 70-90% of carpal tunnel release (CTR) surgeries have good to excellent long-term outcomes,⁴ but, like all operations, there are risks associated with CTR surgery. Some of these risks include injury to the median nerve, its branches, vessels or tendons; infection; and scar sensitivity.⁸ In a review of 186 CTR cases, about 24% of patients experienced mild residual symptoms and 8% experienced recurrent or persistent problems.³

The shortcomings of current conservative treatment options and the fear of invasive procedures, scarring, or return of symptoms after surgery motivate several patients to explore other conservative, non-invasive treatment options.

3.2. Study Device

The study device is a stiffness-optimized thermoplastic curved band that has a strong biocompatible adhesive in the center of the concave side of the device. Similar to other non-invasive devices for CTS, the study device is a Class I device that requires Food and Drug Administration (FDA) registration but does not require 510(k) clearance.

Unlike the majority of traditional and dynamic splints, the study device was developed to decompress the median nerve without excessive applied force and cumbersome usage requirements. The design of the study device allows for free movement of the wrist with minimal impediment of daily activities.

The study device is indicated for people who have been diagnosed with mild to severe carpal tunnel syndrome. It is fit to the subject based on the criteria in the Instructions for Use.

The sham device is similar to the active study device but with a conformable cushion attached to the underside to prevent the main mechanism of action. Neither the sham nor the active study device contain any medicinal substances or electromagnetic properties that could affect human tissue.

The active study device and the sham device should be stored at room temperature.

3.3. Potential Risks & Benefits

3.3.1. Known Potential Risks

Immediate risks related to the device include skin irritation or reaction to the adhesive used on the device, and discomfort related to any forces that the device applies to the wrist.

Previous studies have found the study device can be worn for over 12 hours with little to no discomfort and minor to no redness.⁹

The sham device is the same as the active device but with a cushion on the underside. This cushion is similar to sponges used for make-up or healthcare applications.

3.3.2. Known Potential Benefits

Prolonged wear (anywhere from 1 week to 4 weeks) of the study device may reduce symptoms of CTS.⁹

The sham device may cause a placebo effect and reduce symptoms of CTS as well.

4. Objectives & Endpoints

Objective	Endpoints	Explanation
Primary		
Investigate whether daily wear of the study device significantly reduces patient-reported CTS symptom severity.	Symptom Severity Score (SSS) of the Boston Carpal Tunnel Questionnaire (BCTQ) in the treatment group at 8 weeks compared to Baseline.	The SSS is a validated combined measure of the patient's perception of the level and frequency of pain, numbness, tingling caused by CTS. 8 weeks is the end of the treatment period.
Secondary		
Determine whether there is a difference between the active device group and sham group.	Comparing SSS at 8 weeks and between the active device group and sham group.	Between group comparison conducted for the primary outcome variable at the primary endpoint (8 weeks).

Additionally, we will determine if this difference continues post-treatment.	Comparing SSS 1 month post-treatment (12 weeks) between the active device group and sham group.	Single timepoint at 12 weeks compared between groups for post-treatment analysis.
Exploratory		
Does CTS symptom improvement occur before 8 weeks?	Significant reduction in SSS compared to Baseline at any time point before 8 weeks.	Identification of significant SSS reduction before 8 weeks suggests a shorter minimum duration of wear.
Do unilateral and bilateral CTS patients respond differently to treatment?	Change in SSS at 4 and 8 weeks in a unilateral subgroup compared to a bilateral subgroup.	Unilateral patients showed significant SSS improvement in the pilot study, whereas bilateral patients seemed to show none. ⁹ Both 4- and 8-week timepoints compared in case a difference is seen before the end of treatment.
Do patients respond differently based on Baseline severity?	Change in SSS at 4 and 8 weeks in mild, moderate, and severe subgroups.	AANEM guidelines categorize CTS into 3 severity groups.
Describe the effect of study device treatment on patients with hormonal-induced CTS, such as pregnancy.	Change in SSS at or within 8 weeks in a subgroup of pregnant women.	The study device is hypothesized to work primarily for repetitive stress induced CTS. Pregnant women often develop CTS due to swelling of the tissue.
Demonstrate high subject compliance.	Diary wear time responses. Number of dropouts due to non-compliance.	Compliance is measured by adherence to daily wear and actual vs advised wear time.
Obtain user feedback on the comfort, use, and design of the study device.	User Feedback Survey responses at the end of Treatment Period	Collects qualitative data on practical aspects of the device.

5. Study Design

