5.1. Overall Design

It is hypothesized that daily wear of the study device will result in significant improvements in patient-reported symptom severity. It is also hypothesized that the effects from active study device treatment will be significantly greater than effects from sham treatment. In both cases, it is hypothesized that improvements will be sustained post-treatment.

This study is designed as a randomized, double-blind, sham-controlled, two-arm trial consisting of an eight-week treatment period (active study device or sham), followed by one required follow-up four weeks later (at week 12). After the required follow-up evaluation, the active device group can optionally continue to report symptom changes for an additional 8 weeks. The sham group participants can elect to wear the active study device for 8 weeks after completing their week 12 follow-up evaluation of the sham device. For both groups, completion through the optional follow-ups results in a 5-month patient duration.

There are two study groups: the active device group receiving the active study device and the sham group receiving a non-active sham device. Subjects will be informed that they have a 50:50 chance of receiving treatment or a sham. They will also be informed that if they receive sham device, they will be offered the active device 4 weeks into the post-treatment period. However, all subjects will not know what treatment they are on until the conclusion of the trial. Study devices are shipped directly to enrolled subjects from the Sponsor's designated shipping associate, which blinds site staff to group assignment.

There are (at minimum) three physical research sites but subjects are primarily enrolled remotely. The physical research sites are clinics that local subjects can physically go to if needed (e.g., medical concern, AE). Enrolled subjects are assigned to the PI of the geographically closest physical site.

Subjects are enrolled following confirmation of CTS in one or both wrists via a recent Nerve Conduction Study (NCS) and are asked to wear the assigned device daily for 8 weeks. The NCS is an electrodiagnostic technique used to confirm clinical diagnosis of CTS, with a 56% to 85% sensitivity and at least 95% specificity for CTS.¹⁵ The primary outcome measure, Symptom Severity Score (SSS) of the Boston Carpal Tunnel Questionnaire (BCTQ), is evaluated at:

- Baseline
- Once every 2 weeks during the 8-week treatment period

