10.2. Sample Size Determination

A total of 102 subjects are required for this study, with 51 in each group.

The outcome measure used for calculations in the SSS of the BCTQ, which ranges from 1 to 5 with 1 being no symptoms (improved) and 5 being the worst symptoms (worsened).

A moderate effect size of 0.4 was chosen, assuming that study device efficacy is 0.4 greater than sham.

The pilot study experienced a drop-out rate of 20% (2 out of 13 total). With the longer treatment and follow-up times of this study, a higher drop-out is expected. Therefore the sample size calculation is modified by an estimated attrition rate of 25%.

The primary objective examines the 8 week vs baseline within-active group SSS change. Sample size determination explanation. The power analysis using the above results in a significance level of 0.05 and a power of 0.94*.

The secondary objective examines the change in SSS after 8 weeks between the active study device and sham groups. Sample size calculation is based on a parallel, one-sided t-test power analysis to identify an effect size of 0.4, standard deviation of 0.7 (based on the pilot study PPS-CTMD-15-001), significance level of 0.05, power of 0.8, and an estimated attrition rate of 25%.

The sample size was chosen to meet both the primary and secondary objectives.

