10.5. Statistical Analyses

The primary efficacy endpoint is the improvement (reduction) in SSS of the treatment group at 8 weeks after the first day of device wear. The primary efficacy endpoint will be analyzed using a paired, one-sided t-test.

The secondary efficacy endpoint is the improvement (reduction) in SSS of the treatment group compared to the sham group at T4 (8 weeks after the first day of device wear). The secondary endpoint will be analyzed using a two sample one-sided t-test.

A repeated measures analysis of variance will be used to evaluate changes over time in both the active and sham groups.

The exploratory endpoints will be analyzed using descriptive methods.

Safety analyses will be performed on all subjects that received treatment.

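### The exploratory early-improvement endpoint reads any significant uncontrolled drop in SSS before Week 8 as a hint that shorter wear is enough; placebo response or regression to the mean could readily meet that rule

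*Combined protocol and SAP*

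**What the plan says.** The first exploratory row of the table in Section 4 asks whether symptoms improve before Week 8. Its endpoint is "Significant reduction in SSS compared to Baseline at any time point before 8 weeks". The explanation column adds: "Identification of significant SSS reduction before 8 weeks suggests a shorter minimum duration of wear". The row names no arm, comparator, test, sidedness or significance level.

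Four other places bear on it:

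- Section 3.3.2 accepts that the control can work too: "The sham device may cause a placebo effect and reduce symptoms of CTS as well". No size is given.
- Section 5.1 schedules SSS "Once every 2 weeks during the 8-week treatment period", so there are three visits before Week 8. Section 2.2 marks the BCTQ as required at Weeks 2, 4 and 6 in both arms.
- Section 10.5 states: "The exploratory endpoints will be analyzed using descriptive methods". It also plans a repeated measures analysis of variance over time in both groups, but states no arm-by-visit contrast.
- Section 6.1 requires an SSS of at least 2 for entry. Under Sections 7.2.1 and 7.2.3 the BCTQ completed at enrollment also supplies the baseline.

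**The concern.** A drop from baseline in one arm mixes any device effect with placebo response, natural course and regression to the mean. The last is a live possibility because subjects are admitted on a minimum score of the same scale that supplies the baseline. The rule can be met at any one of three visits, and a conclusion about wear time is written beside it in advance. A reader of the results could credit the device with an early effect that the sham arm shows equally.

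There is a second gap. Every subject is asked to wear the assigned device for the full 8 weeks, so nobody is assigned to stop earlier. An early drop, controlled or not, describes when symptoms change during continued wear. It does not show what happens when wear stops sooner.

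The two sections also disagree. An endpoint defined by significance needs a test, whereas Section 10.5 says that this class of endpoint is only described.

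**Working it through.** **Inputs from the documents.** Section 10.2 gives "A total of 102 subjects are required for this study, with 51 in each group", from a "one-sided t-test power analysis to identify an effect size of 0.4, standard deviation of 0.7", with "significance level of 0.05, power of 0.8, and an estimated attrition rate of 25" percent. Section 5.2 gives pilot changes of 0.59 (SD 0.68) at 4 weeks and 0.79 (SD 0.74) at 12 weeks.

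**Reproducing the plan's sample size.** n per arm = 2 × (1.645 + 0.842)² × (0.7/0.4)² = 37.9, rounded up to 38 completers. Allowing for attrition, 38/(1 − 0.25) = 50.7, so 51 per arm and 102 in total. This matches the plan, so 38 is the number of completers used below.

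**Assumptions not in the documents.**

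- The test is a paired one-sided t-test at 0.05, borrowed from the Week 8 primary analysis.
- The SD of change is 0.7 at each visit.
- The correlation between the changes at different visits is 0.5 to 0.7.
- The size and time course of the non-device drop are as shown in the table.

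**Smallest observed drop that is significant at one visit.** t × SD/√n = 1.687 × 0.7/√38 = 0.19 one-sided, and 2.026 × 0.7/√38 = 0.23 two-sided.

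**Chance of meeting the rule at one or more of Weeks 2, 4 and 6 with no device effect** (simulation, 20,000 to 40,000 trials per scenario; the range covers correlations 0.7 to 0.5 and simulation variation):

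| Non-device drop in SSS | One-sided 0.05 | Two-sided 0.05 |
|---|---|---|
| 0 | 10-12% | not needed |
| 0.1, constant from Week 2 | 37-43% | not needed |
| 0.15, constant | 55-61% | not needed |
| 0.2, constant | 72-79% | 59-66% |
| 0.3, constant | 94-96% | not needed |
| Linear rise to 0.19 at Week 8 | 40-44% | 28-31% |
| Linear rise to 0.39 at Week 8 | 83-86% | 73-76% |

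As a check on the first row, three independent tests would give 1 − 0.95³ = 14%. Positive correlation brings this down to 10-12%.

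**Where the sham response might lie.** Subtracting the assumed advantage over sham from the pilot changes gives 0.59 − 0.4 = 0.19 and 0.79 − 0.4 = 0.39. This is an inference, not a figure in the plan. Held constant from Week 2, these drops meet the one-sided rule in 69-75% and in more than 99% of trials.

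**Does adjusting for three visits cure it?** No. With 0.05/3 per visit and correlation 0.5, the pre-post rule is still met in 55% of trials at a drop of 0.19 and 98% at 0.39.

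**Does the sham comparison cure the attribution problem?** Yes. With 38 per arm and the same placebo response in both arms, an active-versus-sham signal at any of the three visits occurs in about 11-12% of trials unadjusted and about 4% at 0.05/3, whatever the size of that response.

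**The case against.** The strongest reply is that this is one exploratory row, worded cautiously, and that Section 10.5 makes it descriptive. No stopping rule or change in wear schedule depends on it. Whether symptoms improve before Week 8 is a question of timing that within-patient trajectories can fairly describe. An unadjusted look at three visits is no error in a descriptive analysis. If Section 10.5 governs, the error rates above describe a test that nobody will run; if Section 4 governs, the test and its sidedness are borrowed. The plan also has a repeated measures analysis covering both arms.

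Much of this stands. It sets the severity, and it means the lack of multiplicity adjustment is not the point. It does not remove the mismatch between a significance criterion and a descriptive analysis, or the wear-time conclusion attached to an uncontrolled comparison. The repeated measures analysis helps only once an arm-by-visit contrast is stated.

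A reader might infer that placebo response alone would usually trigger the rule. The documents do not support that. They say only that sham may reduce symptoms, and give no size. On the one-sided assumptions the rate passes one half at a constant drop of about 0.15, but stays below it at 0.1 and for a slow rise to 0.19 at Week 8.

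**Conclusion.** The point holds at low severity. The endpoint as written lets an uncontrolled pre-post drop at any of three visits suggest a shorter minimum wear time, and it conflicts with the descriptive analysis in Section 10.5. Non-device change could readily satisfy it. How often depends on an assumed drop: from 10-12% of trials at no change to 94-96% at a constant 0.3, given 38 completers, SD 0.7, correlation 0.5 to 0.7 and a one-sided test that is not specified for this endpoint. Two-sided testing lowers the rates. The design weakness does not depend on any of these figures.

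Two further readings go too far. The trial is not set to declare that shorter wear suffices, because the row only says that a result would suggest it. Nor would an early active-minus-sham difference establish that shorter wear suffices: it improves attribution to the device but leaves the effect of stopping earlier unobserved. The primary and secondary inferences are unaffected.

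**What to change.** - In Section 4, redefine the early-improvement endpoint as the active-minus-sham difference in SSS change from baseline at Weeks 2, 4 and 6, each with a 95% confidence interval and reported descriptively. Drop the significance criterion so that the row agrees with Section 10.5.
- In Section 10.5, state the arm-by-visit contrast within the repeated measures analysis that is already planned. Within-arm trajectories may be shown alongside.
- Delete the sentence in Section 4 that infers a shorter minimum wear time. The design contains no assigned comparison of shorter with full wear.

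The cost is wording plus one stated contrast. The data are already collected in both arms at these visits, and the sample size does not change.

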5.2. Scientific Rationale

The study device was used in a pilot clinical trial (PPS-CTMD-15-001, ClinicalTrials.gov ID NCT02534493) that finished in October 2016 with promising results. Participants showed an average improvement in symptom severity scale (SSS) score of the Boston Carpal Tunnel Questionnaire (BCTQ) of 0.59 ± 0.68 points at 4 weeks (end of treatment period) compared to baseline SSS scores. After the 4-week treatment period, symptoms continued to improve for a total of 0.79 ± 0.74 points lower SSS compared to Baseline at 12 weeks.⁹ These results motivate the primary objective of this study.

The pilot study investigated the effects of the study device up to 4 weeks, but the trajectory of SSS did not indicate that improvement plateaued by 4 weeks. Thus, the treatment period is extended to 8 weeks in this study to determine if improvements continue with longer-term wear.

Analysis of the unilateral vs bilateral CTS patients showed a stark contrast in response. SSS of the unilateral patients improved 0.9 ± 0.5 points at 4 weeks and up to 1.2 ± 0.5 points at 12 weeks. In contrast, the bilateral patients appeared to show no improvement; however, the pilot study was not powered to detect differences in unilateral and bilateral subgroups. This difference is being explored as an exploratory objective in this study.

Most participants described the study device as being very comfortable and easy to wear. However, there were occasional comments about discomfort from the edges of the device. In Aim 1 of the NIBIB grant R44 EB024713-01, a series of experiments were conducted to investigate the applied pressures on wrists using tactile pressure sensors, the changes in median nerve dimensions using magnetic resonance imaging (MRI), and the changes in carpal tunnel or median nerve compression pressures in cadavers when the study device was applied to the wrist. This allowed the study device to be re-designed to fit a wider range of people and to reduce uncomfortable pressure points. A user feedback survey is incorporated in the present study to improve user satisfaction, which is critical for any practical application and success.

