6.1. Inclusion Criteria

1. Ages 21-65
2. Clinically diagnosed with mild to severe carpal tunnel syndrome (CTS)
3. CTS diagnosis confirmed by a nerve conduction study (NCS) performed within the past 24 months OR at enrollment/baseline visit
 - a. CTS severity determined via AANEM criteria¹³
 - b. Bilateral CTS accepted (worse wrist via NCS and/or BCTQ is designated as the study wrist)

4. BCTQ SSS ≥ 2
5. Reliable access to and ability to use Internet, Wi-Fi, or mobile data through computers, mobile devices, laptops, and/or tablets
6. Willing to abstain from any other treatment or therapies for CTS throughout the study
7. Ability to read and write English, or has a reliable person to assist with reading and writing English

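### The exploratory laterality and severity endpoints are raw SSS change by subgroup, with no active-minus-sham contrast, so they cannot by themselves show whether the device effect differs between subgroups

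*Combined protocol and SAP*

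**What the plan says.** The exploratory part of the table in Section 4 (Objectives & Endpoints) asks: "Do unilateral and bilateral CTS patients respond differently to treatment". The matching endpoint is "Change in SSS at 4 and 8 weeks in a unilateral subgroup compared to a bilateral subgroup". The next row asks whether response depends on baseline severity, with the endpoint "Change in SSS at 4 and 8 weeks in mild, moderate, and severe subgroups". Neither row names an arm, and neither mentions a comparison with sham.

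Section 10.5 governs the analysis: "The exploratory endpoints will be analyzed using descriptive methods". The repeated measures analysis of variance in the same section covers change over time in both arms but mentions no subgroup.

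Three other places bear on the point:

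- Section 3.3.2 expects a response without the active mechanism: "The sham device may cause a placebo effect and reduce symptoms of CTS as well".
- Section 6.1 fixes the study wrist in bilateral patients: "Bilateral CTS accepted (worse wrist via NCS and/or BCTQ is designated as the study wrist".
- Section 5.2 gives the origin of the laterality question. In the pilot, "SSS of the unilateral patients improved 0.9 ± 0.5 points at 4 weeks and up to 1.2 ± 0.5 points at 12 weeks", while bilateral patients appeared not to improve. It adds that "the pilot study was not powered to detect differences in unilateral and bilateral subgroups".

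**The concern.** The laterality question is about effect modification: is the benefit of the device over no active device different in the two groups? Change from baseline in each group does not isolate that. Two groups can change by different amounts because their natural course, placebo response or regression to the mean differs, with the device doing the same for both.

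The documents make such differences plausible. A sham response is expected. In bilateral patients the study wrist is chosen as the worse of two, which has no counterpart in unilateral patients. Where SSS enters that choice, a high baseline SSS is partly selected and will tend to fall on re-measurement.

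At stake is the interpretation of an exploratory result. The pilot contrast in Section 5.2 is also reported as change from baseline by subgroup. Repeating that summary could reproduce the pattern without showing whether the device caused it, although this trial has a concurrent randomized sham arm that can separate the explanations.

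**Working it through.** **Inputs from the documents.** Section 10.2: SD 0.7, difference 0.4, one-sided 0.05, power 0.8, attrition 25%, 51 per arm. Section 10.4: analysis of subjects who complete the 8 weeks.

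**Inputs assumed.** The documents do not give the unilateral share *p* (taken as 0.5, range 0.3 to 0.7), the prognostic difference between subgroups *D* (taken as 0.2 and 0.4), or cell-specific SDs (0.7 throughout).

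**The plan's own figure.** n per arm = 2 × 0.7² × (1.645 + 0.842)² / 0.4² = 37.9, so 38 completers. 38 / 0.75 = 50.7, so 51 per arm and 102 in total. This reproduces Section 10.2. The plan gives no figure for any subgroup analysis.

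**What each contrast estimates.** Let *D* be the subgroup difference in change that would occur without any device effect, and *I* the subgroup difference in device effect.

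| Contrast | Estimates |
|---|---|
| Raw change, active arm only | D + I |
| Raw change, arms pooled 1:1 | D + I/2 |
| Active minus sham, differenced between subgroups | I |

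**Standard errors with 38 completers per arm, p = 0.5 (19 per cell).**

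- Overall arm difference: 0.7 × √(2/38) = 0.16
- Subgroup difference, active arm only: 0.7 × √(2/19) = 0.23
- Subgroup difference, arms pooled: 0.7 × √(2/38) = 0.16
- Arm-by-laterality contrast: 0.7 × √(4/19) = 0.32

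**How often a purely prognostic difference would look like a differential response (I = 0).** Two-sided t-test at 0.05. This is an illustration, because the plan contains no such test.

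| Assumed D | Active arm only | Arms pooled | Arm-by-laterality |
|---|---|---|---|
| 0.2 | 14% | 23% | 5% |
| 0.4 | 40% | 69% | 5% |

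A normal approximation gives 14% and 24% at D = 0.2, and 42% and 70% at D = 0.4.

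**Precision of the arm-by-subgroup contrast.** SE = 0.7 × √(2/(38p) + 2/(38(1 − p))).

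- p = 0.5: SE 0.32, 95% CI half-width 1.96 × 0.321 = 0.63.
- p = 0.3 or 0.7: SE 0.35, half-width 1.96 × 0.350 = 0.69.
- Severity, equal thirds assumed, any pair: SE = 0.7 × √(12/38) = 0.39, half-width 1.96 × 0.393 = 0.77.

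For laterality at p = 0.5, two-sided power is about 24% for an interaction of 0.4. It is about 80% for one of 0.9, the size of the pilot contrast if the bilateral change is taken as zero.

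**The case against.** The strongest reply is that Section 10.5 plans only description. There is no subgroup test, alpha or decision rule, so the rejection rates above belong to a test that nobody will run. That is right, and they serve only to show how easily the raw contrast can mislead. Describing the data does not remove the problem, because a table of raw change by subgroup still invites the reading that the subgroups respond differently to the device.

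A reader might infer that the plan leaves the sham arm out of these comparisons. The text does not say so. It names no arm, whereas the primary endpoint in the same table does specify the treatment group. Tables by subgroup and arm would fit the wording, but the contrast between arms is not specified anywhere.

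A reader might also infer that raw change measures prognosis instead of device effect. That goes too far: in the active arm it estimates the sum of the two, so it is confounded and not purely prognostic.

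The severity row is a weaker case than laterality. Its groups come from nerve conduction results under AANEM criteria (Sections 6.1 and 7.2.3), not from SSS. Direct regression to the mean from grouping on the outcome therefore does not arise. Its question also does not refer explicitly to treatment. Natural course and placebo response can still differ by severity.

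Finally, one might fear that the result would redirect the device's target population. No section links the subgroup findings to the indication, which Section 3.2 gives as mild to severe CTS, so that consequence is not supported.

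The objection on precision stands. Randomization is simple, with no stratification stated (Section 10.3), and six arm-by-severity cells would average about 38/3 ≈ 13 completers.

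**Conclusion.** The point holds as a mismatch between question and endpoint. For laterality the plan asks about differential response to treatment and specifies a summary that cannot isolate it; the severity endpoint shares the gap in milder form. Nothing elsewhere in the documents supplies the missing contrast.

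The possible error equals the prognostic difference itself, whose size the documents do not give. The illustrated rates rest on the assumed D and 50/50 split and would change with either. The arm-by-subgroup contrast targets the right quantity but will be imprecise, so it should be read as an estimate and not as a test. Primary and secondary conclusions are unaffected, and priority is low.

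**What to change.** In Section 4, define both subgroup endpoints as the active-minus-sham difference in SSS change within each subgroup (laterality; severity by nerve conduction study) at Weeks 4 and 8. Add the difference of those differences between subgroups, with a 95% CI.

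In Section 10.5, state the model: SSS change on arm, subgroup, arm-by-subgroup and baseline SSS. State also that the results are exploratory and will be read as estimates with intervals, without a significance claim. Raw change by subgroup and arm can stay as a supporting table.

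The cost is a modest amount of extra analysis and wide intervals, widest for severity. Laterality, severity and the BCTQ are already recorded at baseline (Section 7.2.3), so no new data, visits or subjects are needed.
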